In order to carefully define what is considered an adverse event, a retrospective chart review was performed for 15 infants in the past 12 months who survived congenital heart surgery with cardiopulmonary bypass at MMC. Of the 15 infants, the mean age at the time of surgery was 148 days with a range from 4 to 356. Of the 15 infants, 10 were male and 5 female. These infants had a mix of cardiac lesions similar to those who would be enrolled in this study. See Table 1 for a full outline of parameters that will be considered acceptable for infants enrolled in the study, which are based on the retrospective review of 15 survivors. Using these parameters to define what has been previously consistent with “safe”, any infant enrolled in the proposed study with results outside these parameters will then be considered as an adverse event and the data safety monitoring board will be informed. If a severe adverse event occurs in either Phase 1 or Phase 2 of the proposed research protocol, no additional infants will be enrolled and all experimental exposures will be suspended until a decision is made by the DSMB.

Table 1: Definitions of Serious, Moderate and Other Adverse Events

Serious Adverse Events	Reported to DSMB within 24 hours of occurrence
Mortality	Death within 48 hour period following surgery
Need for resuscitation	Need for cardiopulmonary resuscitation within 48 hours of surgery
ECMO after surgery	Persistent need for bypass (ECMO) following surgery; STUDY EXCLUSION CRITERIA
Return to OR on day of surgery	Unexplained hemorrhage prompting return to the OR for exploratory surgery
Stroke or seizures	Ischemic or hemorrhagic stroke OR status epilepticus OR clinical or electrographic seizures
Moderate Adverse Events	Reported to DSMB within 48 hours of occurrence
Bradycardia	Clinically significant heart rate <100 bpm for >30 minutes*
Tachycardia	Clinically significant heart rate > 160 bpm for 30 minutes*
Arrhythmia (JET)	Any occurrence of JET(Junctional ectopic tachycardia) OR other arrhythmia
Hypotension	Systolic BP< 70 mm Hg OR Diastolic BP< 30 mm Hg *
Coagulopathy	INR > 2.2 OR PTT > 74 seconds Thrombocytopenia with platelets < 50,000 Chest tube output more than 5 cc/kg/hr OR 40 cc/kg in an 8 hour shift
Leukopenia	White blood cell count < 4,000
Other adverse Events	Reported to DSMB within 7 days

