Hypertension Pressor Use Days of intubation Infection Subcutaneous fat necrosis	Systolic BP > 100 mmHg OR Diastolic BP > 80 mmHg* Treatment with more than 2 pressors for more than 7 days Intubated for longer than 5 days Occurrence of urinary tract infection, pneumonia OR other wound infection Any occurrence

*resulting in hemodynamic compromise and/or need to administer medications to support heart rate and/or blood pressure

Regarding management of patients with complications from the delayed rewarming intervention, the most likely complication from the delayed rewarming intervention is bradycardia during the 12 hour rewarming period. Given that the post-operative temperature starts at 35°C, the bradycardia is likely to be minor. If bradycardia develops, providers at the bedside will assess the hemodynamic status of the infant. A determination will be made regarding whether or not the bradycardia is resulting in any degree of hemodynamic compromise. Hemodynamic compromise will be defined by bradycardia plus hypotension, poor renal function or oliguria. If there is hemodynamic compromise, then pressors will be titrated to increase the heart rate and blood pressure. These infants are typically already treated with two pressors in the immediate post-operative setting. Rapid rewarming may be considered if increasing pressors does not resolve the issue. In other populations of infants, however, rapid rewarming has been found to increase the severity of adverse events. Specifically, in term newborns with peripheral pulmonary hypertension, rapid rewarming exacerbates their condition by further diverting blood away from the lungs (to the large vascular bed in the skin that was just rapidly rewarmed). For this reason, rapid rewarming would only be used as a second step if pressor titration was not successful.

ANALYSIS

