Stroke or seizures	Ischemic or hemorrhagic stroke OR status epilepticus OR clinical or electrographic seizures
Moderate Adverse Events	Reported to DSMB within 48 hours of occurrence
Bradycardia	Clinically significant heart rate <100 bpm for >30 minutes*
Tachycardia	Clinically significant heart rate > 160 bpm for 30 minutes*
Arrhythmia (JET)	Any occurrence of JET(Junctional ectopic tachycardia) OR other arrhythmia
Hypotension	Systolic BP< 70 mm Hg OR Diastolic BP< 30 mm Hg *
Coagulopathy	INR > 2.2 OR PTT > 74 seconds Thrombocytopenia with platelets < 50,000 Chest tube output more than 5 cc/kg/hr OR 40 cc/kg in an 8 hour shift
Leukopenia	White blood cell count < 4,000
Other adverse Events	Reported to DSMB within 7 days
Hypertension Pressor Use Days of intubation Infection Subcutaneous fat necrosis	Systolic BP > 100 mmHg OR Diastolic BP > 80 mmHg* Treatment with more than 2 pressors for more than 7 days Intubated for longer than 5 days Occurrence of urinary tract infection, pneumonia OR other wound infection Any occurrence

*resulting in hemodynamic compromise and/or need to administer medications to support heart rate and/or blood pressure

Stopping Rules: DSMB has the responsibility of pausing or stopping the trial in the case of 1) any serious adverse event probably or definitely related to study intervention OR 2) two or more unexpected or unanticipated adverse events of same or similar type

Adequacy of sample: We aim to enroll 30 infants and randomize 15 to the standard of care and 15 to the experimental group. With 15 infants in each group, we have determined that we will not have the necessary power to permit definitive analysis of the results, but will use these preliminary data to establish whether or not the treatment is safe and well-tolerated for the design of future, larger adequately powered trials.

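### The Stopping Rules set no prespecified trigger for accumulating non-serious events that the protocol anticipates, most clearly bradycardia with hemodynamic compromise

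*Combined protocol and SAP*

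**What the plan says.** The Stopping Rules, in the Data Safety and Monitoring Plan, make the DSMB responsible for pausing or stopping in two cases. Rule 1 covers a serious event that is judged probably or definitely related to delayed rewarming. Rule 2 covers "two or more unexpected or unanticipated adverse events of same or similar type". Neither *unexpected* nor *unanticipated* is defined.

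Table 1 has three classes: Serious, Moderate and Other. Bradycardia ("Clinically significant heart rate <100 bpm for >30 minutes") and hypotension ("Systolic BP< 70 mm Hg OR Diastolic BP< 30 mm Hg") are Moderate, and both carry a footnote requiring hemodynamic compromise and/or medication support. Coagulopathy is also Moderate. Infection and subcutaneous fat necrosis are Other.

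The paragraph on managing complications, after Table 1, states that "the most likely complication from the delayed rewarming intervention is bradycardia during the 12 hour rewarming period". It then defines compromise and describes its management.

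The text before Table 1, under Anticipated outcomes, contains a separate suspension. After a *severe* event in either phase, "no additional infants will be enrolled and all experimental exposures will be suspended until a decision is made by the DSMB". Table 1 has no class called *severe*.

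Moderate events go to the DSMB within 48 hours and Other events within 7 days, although the narrative says any event is reported within 24 hours. The board reviews events in real time and judges their clinical significance and attribution. The only by-arm comparison described is the chi-square or Fisher's exact test in the Analysis section.

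**The concern.** Safety is the primary outcome, and the study is classed as greater than minimal risk in infants. A plausible unfavourable result is an excess of moderate cooling effects in the experimental arm, with few or no serious events. Each case could be explained on its own, since the protocol says these infants typically already receive pressors. Such an excess is hard to see one report at a time and needs a comparison between arms with denominators. If no rule calls for that comparison, enrolment can continue through a growing imbalance unless the board decides by itself to look for one.

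**Working it through.** **1. Each harm against the two rules.** The plan gives no figure to reproduce here beyond 15 + 15 = 30, which is consistent.

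| Harm | Table 1 class | What the protocol says about expecting it | Rule 1 | Rule 2 |
|---|---|---|---|---|
| Bradycardia with compromise | Moderate | Bradycardia named most likely complication; management of compromise planned | No | No, on plain wording |
| Hypotension with bradycardia | Moderate | Part of the definition of compromise | No | No, on plain wording |
| Hypotension alone | Moderate | Monitored, not called expected | No | Judgement |
| Coagulopathy | Moderate | Listed risk, described as atypical in infants | No | Judgement |
| Infection, pneumonia | Other | Listed risk, pneumonia described as unusual in infants | No | Judgement |
| Subcutaneous fat necrosis | Other | Expected not to occur | No | Two cases would fit |

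**2. How much the expectedness call matters.** Take n = 15 experimental infants and an assumed true rate p. The chance that at least two are affected is 1 − (1−p)^15 − 15p(1−p)^14.
- p = 10%: 1 − 0.206 − 0.343 = 0.451
- p = 20%: 1 − 0.035 − 0.132 = 0.833
- p = 30%: 1 − 0.005 − 0.031 = 0.965 (from unrounded terms)

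If the event type is classed as unexpected, these are the chances that rule 2 is met. If it is classed as expected, the chance is 0 at every p.

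**3. The final test as a backstop** (two-sided Fisher's exact, 15 per arm, assumed alpha 0.05).
- 9/15 versus 3/15 gives p = 0.060.
- With 0/15 in control, significance needs at least 5/15 (p = 0.042). With 2/15 it needs at least 9/15 (p = 0.021).
- Exact power is about 25% for true rates of 20% versus 50%, and about 45% for 20% versus 60%.

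**4. What a by-arm look could do.** As an example, look after 10 and 20 infants and trigger review if affected experimental infants exceed affected controls by 4 or more. With exactly 5 and then 10 per arm, and D the excess at each look, P(fire) = P(D1 ≥ 4) + P(D1 < 4, D2 ≥ 4), from exact binomial enumeration.

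| Control v experimental rate (assumed) | P(fire) |
|---|---|
| 20% v 20% | 0.0023 + 0.0223 ≈ 2.5% |
| 40% v 40% | 0.0094 + 0.0478 ≈ 5.7% |
| 50% v 50% | 0.0107 + 0.0508 ≈ 6.2% |
| 20% v 40% | 0.0327 + 0.1987 ≈ 23% |
| 20% v 60% | 0.1423 + 0.4724 ≈ 61.5% |
| 20% v 80% | 0.3758 + 0.5393 ≈ 91.5% |

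**5. The equal-arms assumption.** The Randomization section describes a random number generator and sequential envelopes, with no blocking. Under simple 1:1 randomization the arms are exactly 5:5 after 10 infants with probability 252/1024 = 25%. Each infant then adds +1 to the excess with probability half the experimental rate, −1 with probability half the control rate, and otherwise 0. Applying the same margin after 10 and 20 infants gives false triggers of about 4%, 12% and 18% at common rates of 20%, 40% and 60%. A raw-count margin therefore has no fixed error rate until the randomization method is known.

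**6. The two suspension texts.** The text before Table 1 acts on a *severe* event with no relatedness test. The Stopping Rules act on a *serious* event and require probable or definite relatedness. If the two adjectives mean the same, an unrelated serious event suspends the study under one text and meets no rule under the other. If they differ, *severe* has no definition, and whether a Moderate event could reach it is unknown.

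**The case against.** The strongest reply is that the Stopping Rules state when the DSMB must act and do not say it may act only then. Three specialist monitors receive every Table 1 event, review study risk in real time and judge attribution, so a discretionary pause is open throughout. This stands. A reader might infer that no number of moderate events could ever pause the trial; the documents do not support that.

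A reader might also infer that every cooling-related harm is anticipated and so lies outside rule 2. That fails too. Fat necrosis is expressly not expected, coagulopathy and pneumonia are described as atypical in infants, and hypotension alone is nowhere called expected. Even for bradycardia, the protocol foresees a minor form, so repeated compromise might be argued to be unanticipated. Against that argument, the same paragraph plans for compromise.

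Nor do the documents say that by-arm counts are withheld from the DSMB. They are silent on report format, and the board could tally the reports itself.

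Escalation is partly covered: death, resuscitation, return to the operating room for unexplained hemorrhage, stroke and seizures are Serious. Rule 1 then applies, but only after worse harm and a relatedness judgement.

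Finally, a formal boundary in a 30-infant pilot that disclaims power may be called a design preference. That is fair for a strict statistical boundary. It does not answer the lack of any scheduled comparison in a study whose primary outcome is safety by arm.

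**Conclusion.** The point holds in limited form. No prespecified trigger covers accumulating non-serious events that the protocol anticipates. The clearest case is bradycardia with compromise, where the chance that either numbered rule compels a pause is 0 at any frequency if it is classed as expected. For coagulopathy, infection and hypotension alone, the reach of rule 2 depends on an undefined term; at assumed true rates of 10-30% that term decides between 0 and 45-97%. The two suspension texts do not agree.

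The gap is in what is prespecified, and the board's power to act remains. All event rates and the 0.05 level are assumptions, because the documents give none for safety. The finding on wording does not depend on them. The change should be made, since it is cheap and bears on patient safety.

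**What to change.** 1. After about 10 and 20 infants, give the DSMB a cumulative table by arm, with denominators, of infants with at least one Serious or Moderate Table 1 event.
2. Add a review trigger fixed in advance by the sponsor and DSMB. Base it on the difference in proportions, or on counts given the actual arm sizes, and compute its error rates for the randomization actually used. The 4-infant margin above is only an illustration.
3. State which Table 1 events count as expected for rule 2.
4. Reconcile the suspension text before Table 1 with the Stopping Rules, using defined terms and one stated position on relatedness. The choice belongs to the sponsor and DSMB.

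The cost is two short tables for an existing board, a paragraph of text and some chance of an unnecessary review. For the illustrative margin that chance is about 2-6% if arms are exactly equal at each look, and about 4-18% under simple randomization, at assumed common event rates of 20-60%.
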